7.11 Cohorts 1-3 secondary outcomes

Unless otherwise specified, these analyses will follow the approach for the primary efficacy outcomes.

7.11.1 Changes in plasma HIV-1 RNA levels as detected by single copy assay from baseline to 6 and 12 hours, and 7, 14, and 28 days after the administration of RMD or placebo.

Included in the analysis of 7.10.1

7.11.2 Change in cell-associated HIV-1 RNA levels in resting CD4+ T-cells from baseline to 14 days after the administration of RMD or placebo.

Included in the analysis of 7.10.2

- 7.11.3 Changes in cell-associated HIV-1 RNA levels in total CD4+ T-cells from baseline to 6, 12, 24 and 48 hours, and 7, 14, and 28 days after completion of RMD or placebo.
- 7.11.4 Changes in histone acetylation in total CD4+ T-cells by flow cytometry from baseline to 12, 24, 48 hours and 7 and 14 days after the administration of RMD or placebo.

NOTE: Mean and median FI records with sample acquisition counts < 10,000 will be excluded from the analysis.

Outcomes of interests: FICD3MED; FICD3MN, FICELMED, FICELMN

May 7, 2018

a. Tables:

- Completeness of data for all measurement time points
- Summaries for each outcome at each measurement time point: N, median, 25th and 75th percentiles, min, max
- Summaries for each outcome's absolute change from baseline to each measurement time point: N, median, 25th and 75th percentiles, min, max

Wilcoxon rank sum tests will be used for the comparisons of change (from pre-dose) between groups.

b. Figure:

Longitudinal, participant-specific, (spaghetti) plots for all measurement time points using different panels/symbols/colors for RMD and placebo, separately for each cohort.

Median (change from pre-dose) plots for combined cohorts and placebo groups.

- 7.11.5 Changes in total HIV-1 DNA and 2-LTR circles in resting or total CD4+ T-cells from baseline to 6, 12, 24, and 48 hours and 7, 14, and 28 days after the administration of RMD or placebo.
- 7.11.6 Pharmacokinetic parameters (AUC, Cmax, Cmin) for RMD and co-administered antiretroviral drugs (EFV, DTG, or RAL).

Table summarizing of the pharmacologist-estimated PK parameters.

7.11.7 Number/percent of subjects with HIV-1 RNA levels > 200 copies at the Day 7 visit

See 7.7

7.11.8 All reported Grade 2-4 AEs.

List showing all the events with grade 2-4 for each study participant. The list will include the following:

- public ID
- treatment dispensation date
- visit week
- onset date
- resolution date
- event description
- value and units (for laboratory results)
- grade

7.12 Cohorts 1-3 exploratory outcomes

Unless otherwise specified, these analyses will follow the same approach for the primary efficacy outcomes.

- 7.12.1 Change in CD4+ and CD8+ T cell percent from baseline to 48 hours, 7, and 28 days after the administration of RMD or placebo.
- 7.12.2 Changes in the percentage of CD3+ CD4+ and CD3+ CD8+ lymphocytes and cellular markers of immune activation (CD38/HLA-DR or CD69/CD25 expression on CD4+ and CD8+ T-cells) from baseline to 48 hours, and 7 and 28 days after the administration of RMD or placebo.
- 7.12.3 Changes in proportion of cycling CD4+ and CD8+ T-cells (Ki67 expression) from baseline to 48 hours,7, and 28 days after the administration of RMD or placebo.
- 7.12.4 Changes in the levels of soluble markers IL-6, C-reactive protein (CRP), and D-dimer from baseline to 7 and 28 days after the administration of RMD or placebo.
- 7.12.5 Percentage of total lymphocytes expressing annexin V and 7 amino-actinomycin D (7-AAD) at baseline,
 48 hours, 7 and 28 days after the administration of RMD or placebo.
- 7.12.6 Changes in ex vivo PMA/Ionomycin and RMD inducible HIV-1 RNA expression in resting CD4+ T-cells from baseline to 14 days after RMD dosing.
- NOTE: Undetected values will be imputed with a value of 20 copies/mL; these are represented in the database as "< .".

Outcomes of interests: untreated (Y_{UNT}), PMA-treated (Y_{PMA}), and RMD-treated (Y_{RMD}). These Y variables will be average of the log transformed replicates, as long as the number of replicates is \geq 3. Note that data with replicate number < 3 will be excluded from the analyses.

a. Tables:

- Completeness of data for all measurement time points (no data, < 3 replicates and ≥ 3 replicates)
- Summaries for each outcome at each measurement time point: N, median, 25th and 75th percentiles, min, max
- Summaries for ratio of RMD-treated/untreated and PMA-treated/untreated at each measurement time point: N, median, 25th and 75th percentiles, min, max.
 - Ratio_{PMA} = $exp(Y_{PMA})/exp(Y_{UNT})$, Ratio_{RMD} = $exp(Y_{RMD})/exp(Y_{UNT})$, repeat for baseline and day 14.
- Summaries for each outcome fold change from baseline to week2 (week 2/pre-dose): N, median, 25th and 75th percentiles, min, max
 - \circ FC(Y_{UNT}) = exp(Y_{UNT at day 14})/ exp(Y_{UNT at baseline}), repeat for PMA and RMD
 - FC(PMA) = (Ratio_{PMA at day 14})/(Ratio_{PMA at baseline}), repeat for RMD

Wilcoxon rank sum tests will be used for the comparisons between groups.

b. Figure:

Longitudinal, participant-specific, (spaghetti) plots for all measurement time points using different symbols/colors for RMD and placebo.

7.12.7 Changes in P-TEFb and HIV-1 expression; changes in PTEF-b phosphorylation in total CD4+ T-cells by flow cytometry from baseline to 12, 24, 48 hours and 7 and 14 days after the administration of RMD or placebo.

7.13 Cohort 4 primary efficacy outcomes

7.13.1 Change in plasma HIV-1 RNA levels from baseline (average of pre-entry and entry values) as detected by single copy assay before and 24 hours after each administration of RMD or placebo in Cohort 4.

The analysis of 7.13.1 will be combined with 7.14.1. The available timepoints are: pre-entry (-35 to -28 days), pre- & 24hr post-infusion for all 4 infusions, and 72hr post-2nd-infusion

SCA values below the limit of detection (LOD) will be imputed as equal to half the limit of detection (i.e., if LOD=0.4 copies/mL, results < 0.4 copies/mL will be imputed as 0.2 copies/mL).

a. Tables:

- Completeness of data for all measurement time points
- N (%) of SCA value < LOD at all measurement time points
- Baseline SCA: N, median, 25th and 75th percentiles, min, max
- Pre- and 24hr post-infusion SCA for each infusion and 72hr post-2nd-infusion: N, median, 25th and 75th percentiles, min, max
- Change (at each post-entry time point baseline) SCA: N, median, 25th and 75th percentiles, min, max
- Change (post-infusion time point pre-infusion time point for each infusion) SCA: N, median, 25th and 75th percentiles, min, max

NOTE: Baseline averages will be calculated using log10-transformed SCA values.

Wilcoxon rank sum test will be used for the comparison between groups. Wilcoxon signed rank test will be used to test within-group changes for RMD group. Two-sided 95% confidence intervals for the shift will be calculated based on Hodges-Lehmann estimator.

b. Figure:

- Longitudinal median (Q1, Q3) plots for all measurement time points by RMD and placebo.
- Longitudinal, participant-specific, (spaghetti) plots for all measurement time points with open symbol for values below the LOD and different symbols/colors for RMD and placebo.

7.13.2 Change in cell-associated HIV-1 RNA levels in PBMCs before and 24 hours after each administration of RMD or placebo in Cohort 4.

The analysis of 7.13.2 will be combined with 7.14.2. The available timepoints are the same as 7.13.1 and 7.14.1. The same analysis approach will be used as in 7.13.1 (except N (%) below LOD).

NOTE: Cell-associated RNA results below the detection limit are imputed with 1 copy/million PBMCs.

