6.3.9 Immunologic Studies

CD4+/CD8+ (Cohorts 1 – 3 only)

For Cohorts 1-3 only, obtain absolute CD4+/CD8+ T cell count and percentages within 90 days prior to entry from a laboratory that possesses a CLIA (Clinical Laboratory Improvement Amendments) certification or equivalent.

CD4+ (Cohort 4 only)

At screening, obtain absolute CD4+ cell count between 36 and 60 days prior to study entry performed at a laboratory that possess CLIA certification or equivalent.

CD4+ percentages

At the time points indicated in the SOE, obtain CD4 percentages only **performed at** a laboratory that possess CLIA certification or equivalent.

During the study, all laboratories must possess a CLIA certification or equivalent and must be qualified for protocol testing by the DAIDS Immunology Quality Assurance (IQA) Program.

Stored Plasma/PBMC for Immunology Studies

Cryopreserved PBMC obtained by blood draw will be stored for T cell analysis per the SOE. Specific lymphocyte marker testing will include the following:

- Proportion of CD4+ and CD8+ T cells co-expressing CD38/HLA-DR or CD25/CD69
- Percentage of CD3+ lymphocytes that are CD4+ and CD8+
- Proportion of CD4+ and CD8+ T cells that are in cell cycle (Ki-67+)
- Percent of total lymphocytes expressing Annexin V alone and those expressing both Annexin V and 7-AAD

Plasma samples will be obtained to test for the levels of soluble markers of inflammation including IL-6 and hsCRP.

D-dimer (Cohorts 1 – 3 only)

Citrated plasma samples will be obtained per the SOE to test for the levels of Ddimer.

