9.2 Outcome Measures

NOTE: Due to insufficient numbers of resting CD4+ T-cells available from some Cohort 4 participants to perform all the planned assays (e.g., cell-associated HIV-1 RNA, total HIV-1 DNA, histone acetylation, PTEF-b activation), those assays will be performed using peripheral blood mononuclear cells (PBMCs). The team carefully reassessed the priorities for the use of these cells based on advances in the field since the prior protocol version. Accordingly, the relevant objectives and outcomes measures sections have been updated.

- 9.2.1 Primary Endpoints
 - 9.2.1.1 Safety

Occurrence of Grade \geq 3 AE including signs/symptoms, lab toxicities, and /or clinical events that is probably, possibly or definitely related to study treatment (as judged by the core team, blinded to treatment arm) any time from the time of study treatment administration until 28 days after the administration.

- 9.2.1.2 Efficacy
 - 9.2.1.2.1 Change in plasma HIV-1 RNA levels from baseline (average of pre-entry and entry values) as detected by single copy assay at 24 and 48 hours (average) after the single administration of RMD or placebo in Cohorts 1 3.
 - 9.2.1.2.2 Change in plasma HIV-1 RNA levels from baseline (average of pre-entry and entry values) as detected by single copy assay before and 24 hours after each administration of RMD or placebo in Cohort 4.
 - 9.2.1.2.3 Change in cell-associated HIV-1 RNA levels in resting CD4+ T-cells from baseline to 24 hours after the single administration of RMD or placebo in Cohorts 1 – 3.
 - 9.2.1.2.4 Change in cell-associated HIV-1 RNA levels in **PBMCs** before and **24 hours** after each administration of RMD or placebo in Cohort 4.
- 9.2.2 Secondary Outcome Measures
 - 9.2.2.1 Changes in plasma HIV-1 RNA levels as detected by single copy assay from baseline to after the single administration of RMD or placebo in Cohorts 1 3 and after each administration of RMD or placebo in Cohort 4.

- 9.2.2.2 Change in cell-associated HIV-1 RNA levels in resting CD4+ T-cells from baseline to 14 days after the administration of RMD or placebo in Cohorts 1-3, and in PBMCs after each administration of RMD or placebo in Cohort 4.
- 9.2.2.3 Changes in histone acetylation in CD4+ **and CD8+** T-cells from baseline to after the single administration of RMD or placebo in Cohorts 1-3 and after each administration of RMD or placebo in Cohort 4.

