- 9.2.2.4 Changes in total HIV-1 DNA in resting or total CD4+ T-cells from baseline to after the single administration of RMD or placebo in Cohorts 1 3 and in PBMCs after each administration of RMD or placebo in Cohort 4.
- 9.2.2.5 Pharmacokinetic parameters for RMD and co-administered antiretroviral drugs (EFV, DTG, or RAL).
- 9.2.2.6 Number/percent of participants in Cohorts 1 3 with HIV-1 RNA levels ≥200 copies at the Day 7 visit
- 9.2.2.7 Number/percent of participants in Cohort 4 with HIV-1 RNA levels ≥200 copies/mL at scheduled post-infusion 4 visits.
- 9.2.2.8 All reported Grade 2-4 AEs.
- 9.2.2.9 Change in CD4+ T cell percent from baseline to after each administration of RMD or placebo in Cohort 4.
- 9.2.2.10 Change in CD4+ and CD8+ T cell percent from baseline to after the single administration of RMD or placebo in Cohorts 1 3 and after each administration of RMD or placebo in Cohort 4.
- 9.2.2.11 Changes in the percentage of CD3+ CD4+ and CD3+ CD8+ lymphocytes and cellular markers of immune activation (CD38/HLA-DR or CD69/CD25 expression on CD4+ and CD8+ Tcells) from baseline to after the single administration of RMD or placebo in Cohorts 1 – 3 and after each administration of RMD or placebo in Cohort 4.
- 9.2.2.12 Change in percentage of total lymphocytes expressing annexin V and/or 7 amino-actinomycin D (7-AAD) from baseline to after the single administration of RMD or placebo in Cohorts 1 – 3 and after each administration of RMD or placebo in Cohort 4.
- 9.2.2.13 Changes in P-TEFb and HIV-1 expression; changes in PTEF-b phosphorylation in CD4+ and CD8+ T-cells from baseline to after

the single administration of RMD or placebo in Cohorts 1 - 3 and after each administration of RMD or placebo in Cohort 4.

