7.14 Cohort 4 secondary outcomes

7.14.1 Changes in plasma HIV-1 RNA levels as detected by single copy assay from baseline to after each administration of RMD or placebo in Cohort 4.

NOTE: Only 72hr post-2nd-infusion time point was tested for the primary analysis. Testing of remaining samples is pending on further team discussion.

Included in the analysis of 7.13.1.

7.14.2 Change in cell-associated HIV-1 RNA levels in PBMCs from baseline to after each administration of RMD or placebo in Cohort 4.

NOTE: Only 72hr post-2nd-infusion time point was tested for the primary analysis. Testing of remaining samples is pending on further team discussion.

Included in the analysis of 7.13.2.

7.14.3 Changes in histone acetylation in CD4+ and CD8+ T-cells from baseline to after each administration of RMD or placebo in Cohort 4.

The same analysis approach will be used as in 7.13.2.

7.14.4 Changes in total HIV-1 DNA in PBMCs from baseline to after each administration of RMD or placebo in Cohort 4.

The same analysis approach will be used as in 7.13.2.

Analysis of RNA/DNA ratio will be using the same approach.

7.14.5 Pharmacokinetic parameters for RMD and co-administered antiretroviral drugs (EFV, DTG, or RAL).

Table summarizing of the pharmacologist-estimated PK parameters.

7.14.6 Number/percent of participants in Cohort 4 with HIV-1 RNA levels ≥200 copies/mL at scheduled postinfusion 4 visits.

See 7.7

7.14.7 All reported Grade 2-4 AEs.

List showing all the events with grade 2-4 for each study participant. The list will include the following:

- public ID
- treatment dispensation date
- visit week
- onset date
- resolution date
- event description
- value and units (for laboratory results)
- grade
- 7.14.8 Change in CD4+ T cell percent from baseline to after each administration of RMD or placebo in Cohort4.
- 7.14.9 Changes in the percentage of CD3+ CD4+ and CD3+ CD8+ lymphocytes and cellular markers of immune activation (CD38/HLA-DR or CD69/CD25 expression on CD4+ and CD8+ T-cells) from baseline to after each administration of RMD or placebo in Cohort 4.
- 7.14.10 Change in percentage of total lymphocytes expressing annexin V and/or 7 amino-actinomycin D (7-AAD) from baseline to after each administration of RMD or placebo in Cohort 4.
- 7.14.11 Changes in P-TEFb and HIV-1 expression; changes in PTEF-b phosphorylation in CD4+ and CD8+ Tcells from baseline to after each administration of RMD or placebo in Cohort 4.

For 7.14.8-7.14.11:

Tables:

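### Cohort 4 cell-associated RNA and DNA are analysed per million PBMCs with no analysis scaled to CD4 content, so a romidepsin effect on the CD4 share would shift both results

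*SAP*

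**What the plan says.** **Endpoint and unit.** Protocol 9.2.1.2.4 defines the Cohort 4 endpoint as change in cell-associated RNA in PBMCs from before to 24 hours after each infusion. Protocol 9.2 gives the reason for moving away from resting CD4+ T-cells, the material used in Cohorts 1-3: "Due to insufficient numbers of resting CD4+ T-cells available from some Cohort 4 participants to perform all the planned assays". SAP 7.13.2 confirms the unit: "NOTE: Cell-associated RNA results below the detection limit are imputed with 1 copy/million PBMCs".

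**Analysis.** Apart from the count below the detection limit, SAP 7.13.2 takes over the approach of 7.13.1. That is a rank-sum comparison of romidepsin with placebo and Hodges-Lehmann intervals, and "Wilcoxon signed rank test will be used to test within-group changes for RMD group". The time points are also those of 7.13.1: "The available timepoints are: pre-entry (-35 to -28 days), pre- & 24hr post-infusion for all 4 infusions, and 72hr post-2nd-infusion". SAP 7.14.4 applies the same approach to total DNA in PBMCs and adds: "Analysis of RNA/DNA ratio will be using the same approach". No CD4 term appears in SAP 7.13.2, SAP 7.14.4 or protocol 9.6.

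**Power.** Protocol 9.4.2 gives 80% power for a 0.79 log10 difference with 12 v 3, in copies per million CD4 cells. The SD of 0.33 is stated for resting CD4+ T-cells.

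**CD4%.** It is a separate secondary outcome (9.2.2.9): "Change in CD4+ T cell percent from baseline to after each administration of RMD or placebo in Cohort 4". Protocol 6.3.9 says: "At the time points indicated in the SOE, obtain CD4 percentages only". The Cohort 4 schedules (Tables 6.1.3-1, 6.1.3-2, 6.1.4-1 and 6.1.4-2) mark it at Day -14 to -3, at each infusion visit, and 24 and 72 hours after each infusion. They do not mark it at Day -35 to -28.

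**The concern.** The hypothesis (protocol 1.1) is about expression in latently infected cells, which protocol 2.1 describes as memory CD4+ T-cells. PBMCs are a mixture. Copies per million PBMCs can change because expression per infected cell changed, or because the mixture now holds more or fewer CD4+ T-cells. Randomisation does not separate the two if romidepsin itself alters the mixture. The plan leaves that open, since CD4% change and lymphocyte apoptosis are both Cohort 4 outcomes.

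At stake is a primary endpoint. A fall in CD4 share could mask true induction or look like a decrease in HIV RNA. A rise could look like induction. For total DNA, a fall in CD4 share could be taken for a loss of infected cells.

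**Working it through.** **1. The plan's own figure.** For 12 v 3, SD 0.33, two-sided 5% and 80% power, the detectable difference is 0.60 log10 (normal), 0.65 (t) or about 0.69 (exact Wilcoxon). The stated 0.79 is larger, so it errs on the cautious side. At 0.79 the exact Wilcoxon test has about 89% power. The companion 0.38 for 36 v 9 does reproduce (t with n/1.15 gives 0.379). Nothing below rests on 0.79 being right or wrong. What matters is its unit, which is per million CD4 cells and not per million PBMCs.

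**2. The shift.** Assume the HIV RNA in PBMCs comes from CD4+ T-cells. Then copies per PBMC = copies per CD4+ cell × CD4 fraction, so

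Δlog10(per PBMC) = Δlog10(per CD4+ cell) + log10(CD4% after / CD4% before).

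The last term for assumed relative changes is log10(0.90) = -0.046, log10(0.75) = -0.125, log10(0.60) = -0.222 and log10(1.25) = +0.097.

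**3. Effect on the tests.** Simulation with normal log10 changes, SD 0.33, the same CD4 shift in every romidepsin participant, exact tests at two-sided 5%, and no true change per CD4+ cell:

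| Assumed change in CD4% | Shift (log10) | Signed rank, n=12 | Rank sum, 12 v 3 |
|---|---|---|---|
| none | 0 | 4% | 5% |
| 10% fall | -0.05 | 6% | 5% |
| 25% fall | -0.12 | 19% | 7.5% |
| 40% fall | -0.22 | 52% | 15% |
| 25% rise | +0.10 | 13% | 7% |

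Under the falls, signed-rank rejections in the direction of induction are only about 0.7%, 0.1% and 0%. The rest are spurious decreases. Under the 25% rise, nearly all rejections are false induction.

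**4. Lost power.** With a true +0.30 log10 per CD4+ cell, signed-rank power is 77% with no shift, about 35% with a 25% fall and 10% with a 40% fall. With a true +0.79, rank-sum power goes from 89% to 80% at a 20% fall and to about 51% at a 50% fall.

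**5. What the RNA/DNA ratio does.** Both assays are on PBMCs, so in Δlog10(RNA/DNA) the CD4 term appears twice with opposite signs and cancels. What remains is the RNA change per CD4+ cell minus the DNA change per CD4+ cell. It isolates expression only if the second part is stable, and it says nothing about DNA itself.

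**6. Which CD4% is available.** The RNA time points number 1 + 4 + 4 + 1 = 10. The schedules cover nine of them, all but Day -35 to -28. The list of tested time points under SAP 7.14.8-7.14.10 matches only four of the ten (Day -35 to -28, 24 hours after infusion 1, before infusion 4, 24 hours after infusion 4), which gives a pre/24-hour pair for infusion 4 alone. That list includes Day -35 to -28, where the schedule marks no CD4%. The two may therefore be different measurements.

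**The case against.** The endpoint was defined in PBMCs openly and for a stated reason, so the SAP is carrying out the protocol. This stands: another normalisation is a sensitivity analysis and not the repair of an error.

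The SAP already offers protection. The RNA/DNA ratio cancels CD4 content, and CD4% and apoptosis are analysed in their own right, so a shift would be seen. A reader might infer that every change in CD4% will be reported as a change in HIV expression. The documents do not support that, because the SAP sets no such reading rule and plans the ratio. But the ratio is secondary, assumes stable DNA per CD4+ cell, and leaves the DNA outcome uncorrected. Reporting CD4% separately shows that a shift occurred without removing it from the RNA result.

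No CD4% shift is documented. The bone marrow suppression in protocol 2.2 comes from lymphoma use at the maximum tolerated dose, and the protocol puts 5 mg/m² at 35% of that. This also stands: the percentages are assumptions.

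Protocol 9.6 names only the rank-sum test for the primary comparison, and that test is little affected. This stands too. The SAP does add the signed-rank test, and with three placebo participants the within-group result is likely to carry weight.

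**Conclusion.** The concern holds in a limited form. The per-PBMC analyses of RNA and DNA carry a one-for-one log-scale shift if romidepsin changes the CD4 share. The unit no longer matches the one in which the detectable difference is stated, and no CD4-scaled analysis is planned although nearly all the data are scheduled.

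The size is a range. Assumed falls of 10-40% take signed-rank rejection from about 4% to 6-52%, and rank-sum rejection from about 5% to 5-15%. A reader might take the 52% as the chance of falsely claiming induction. It is not: those rejections are decreases. False induction needs a rise, and an assumed 25% rise gives about 13%.

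The figures rest on SD 0.33 carried over from resting CD4+ T-cells, since no PBMC value is given. They also assume normal changes, a uniform CD4 shift, and one test at a time. With an SD of 0.45 the signed-rank rates for the falls would be about 6%, 12% and 31%. No SD is given for DNA, so the rates should not be carried over to it.

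**What to change.** In SAP 7.13.2 and 7.14.4, pre-specify a sensitivity analysis in which each value is divided by the same-visit CD4 fraction before taking log10. Give it its own rank-sum, signed-rank and Hodges-Lehmann results, and show it beside the per-PBMC result and the RNA/DNA ratio. Base any statement about expression per CD4+ cell on the normalised result. In the simulation, testing the normalised value directly returns signed-rank rejection to about 4%, with CD4% taken as free of error.

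A rule that the two versions must agree in direction would not do the job. False rejections drop only from 19% to 18% (25% fall) and from 52% to 39% (40% fall), because both versions share the same noise.

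Name the clinical-laboratory CD4% from the schedule of evaluations as the source, and reconcile it with the tested time points listed under SAP 7.14.8-7.14.10. For the Day -35 to -28 sample use the Day -14 to -3 CD4%, which assumes it is stable before treatment.

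The cost is SAP text and a few lines of code, with no new samples. The drawbacks are that the scaling is approximate, because PBMCs include monocytes and the documents do not state the denominator of CD4%, and that it adds CD4% measurement noise.
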